### Study groups

*Group 1:* Screening using biennial FIT (latex agglutination, OC-Sensor®, cut-off point: 75 ng Hb/ml), and performance of colonoscopy in patients with a positive result.

*Group 2:* Screening using one-time colonoscopy.

The study design allowed for cross-over between both screening strategies.

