#### 4.4. Study groups, randomisation, and stratification

Asymptomatic men and women aged 50 to 69 years from each participating Autonomous Region will be identified through the corresponding Community Health Registry (CHR) for enrolment into this study. Randomisation will be carried out prior to invitation, with computer-generated lists in blocks of 4 (block randomisation) from the list of health cards, after having previously grouped individuals by household (specified by street address, floor, and apartment number) (see Processes of selecting and inviting the population to be screened section).

All eligible patients will be randomised (1:1 ratio) to the two study groups:

Group 1: Screening by biennial FIT (latex agglutination, OC-Sensor®, cut-off point: 75 ng Hb/ml, corresponding to 15 µg Hb/g of feces), and colonoscopy (after no more than 1 month) for patients with a positive result. Determination of FIT will be made using a single faecal sample, without dietary restriction or interruption of normal treatment of the individual, although the habitual use (>1 month) or recent use (last 7-15 days) of NSAIDs, aspirin, anti-platelet drugs and anticoagulants will be recorded. The above-mentioned cut-off point was used in the baseline round; in subsequent rounds, we decided to modify the cut-off to 20 µg Hb/g of feces since it is the one accepted in the Spanish population-based CRC screening program.

Group 2: Screening by one-time colonoscopy. The ongoing use (>1 month) or recent use (last 7-15 days) of NSAIDs, aspirin, anti-platelet drugs and anticoagulants will also be recorded.

Individuals in Group 1 or Group 2 who do not agree to the type of testing assigned to them may require receiving the alternative test and must still be followed up in order to carry out efficacy analysis according to the intention to screen analysis. The choice of the alternate test will not be actively offered to individuals invited to the study and, accordingly, COLONPREV is not considered a study of sequential screening test offers.

Information on the long-term status of individuals in Group 1 or Group 2 who do not agree to participate in the study will be obtained through population-based registries at the completion of the trial in order to assess efficacy according to the intention to screen analysis.

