- Participants in either Group 1 or Group 2 in whom only 1 or 2 non-advanced adenomas (low-risk adenomas) are detected, will be included in a surveillance programme and offered a new colonoscopy at 5 years.
- Participants in either Group 1 or Group 2 in whom 3 or more non-advanced adenomas or 1 or more advanced adenomas (high-risk adenomas) are detected will be included in a surveillance programme and offered a new colonoscopy after 3 years.
- Participants in either Group 1 or Group 2 in whom >10 adenomas are detected in a single examination will be scheduled for surveillance colonoscopy in less than 3 years.
- Participants in either Group 1 or Group 2 in whom a large sessile adenoma is detected and removed by piecemeal resection will undergo a colonoscopy in 2-6 months to verify complete removal.

- The interval between subsequent surveillance colonoscopies will depend on the findings of the earlier examinations. In general, if a neoplastic lesion is detected, the above-mentioned criteria will be applied. On the other hand, if the examination is normal or if only non-neoplastic disease is detected, the next colonoscopy will be performed 5 years later.
- For participants in either Group 1 or Group 2 in whom a malignant polyp is detected (pT1N0M0) and for whom endoscopic polypectomy is deemed sufficient (see criteria below), a new colonoscopy will be performed with biopsy of the resected area within a period of no more than 2-3 months to confirm that complete resection of the lesion was achieved. Subsequently, new colonoscopies will be performed after 1 and 3 years.
- Participants in either Group 1 or Group 2 in whom an invasive CRC is detected will be treated and followed up according to the specific protocol of each centre, but always including a colonoscopy 1 year after the resection, and every 3 years thereafter.

Any individual may refuse the screening examination assigned and request an alternative method. Any such individual will be assessed according to the group to which he/she was randomised for the “intention to screen” analysis, and according to the procedure actually performed in the “as-screened” analysis. These same criteria will be applied when any screening examination is performed (FOBT, colonoscopy, CT-colonography, or colonic capsule) and that is not foreseen in the study, regardless of the reason.

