## 6. DEFINITIONS

- *Pragmatic study*: study designed to clarify whether an intervention works under real-life conditions and whether it works in terms that matter to the patient. It is simply concerned with whether the intervention works, not how or why.
- *Target population*: 50-69 year-old individuals with verified address in sanitary card.
- *Invited population*: target population excluding non-contacted individuals.
- *Eligible population*: target population excluding non-contacted and excluded individuals.
- *Participant population*: individuals who returned the FIT test (Group 1) or who completed colonoscopy (Group 2).
- *Screening inclusion data*: data of sending the invitation letter.
- *Incomplete colonoscopy*: colonoscopy in which caecal intubation is not possible. When an incomplete colonoscopy occurs, this examination must be repeated or completed with a CT-colonography.
- *Inadequate colon cleansing*: when less than 90% of colorectal mucosa can be properly evaluated due to the presence of faeces, this examination must be repeated.
- *Non-neoplastic polyp*: hyperplastic, hamartomatous or inflammatory polyps.
- *Non-advanced adenoma*: any tubular adenoma <1 cm and with low-grade dysplasia.
- *Advanced adenoma*: adenoma >1 cm in size, or with high-grade dysplasia, or with villous component (>25%).
- *High-risk adenoma*: 3 or more non-advanced adenomas, or any advanced adenoma.
- *Low-risk adenoma*: 1 or 2 non-advanced adenomas.
- *Non-invasive colorectal cancer*: colorectal carcinoma without submucose invasion (pTis). It includes intramucous carcinoma and intraepithelial carcinoma.
- *Invasive colorectal cancer*: colorectal carcinoma beyond the *muscularis mucosa* (pTNM stages I, II, III and IV).
- *Advanced neoplasia*: colorectal advanced adenoma or cancer.
- *Malignant polyp*: adenoma that harbours an area of carcinoma invading submucose (pT1).
- *Polyposis*: existence of >10 polyps. Depending on the histology, it could be adenomatous, hamartomatous or hyperplastic.
- *Non-neoplastic colorectal diseases*: any non-neoplastic disease detected in the colonoscopy (i.e. haemorrhoids, diverticulosis, angiodyplasia, etc.).

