## 7. STATISTICAL ANALYSIS PLAN (SAP)

Because of the study design, which allows for cross-over between both strategies, the main outcomes of the study will be analysed by intention-to-screen, as-screened and per-protocol.

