#### Secondary end points:

1. *Participation, detection rate, diagnostic yield and complication rate at the completion of the first round and at the end of study (10 years)*

Definitions of these four key outcomes are as follows:

- Participation: number of participating individuals (i.e. individuals who completed colonoscopy in the colonoscopy group and individuals who returned the test in the FIT arm) relative to the number of eligible individuals.
- Detection rate: number of true positives relative to the number of participating individuals.
- Diagnostic yield: number of true positives relative to the number of eligible individuals.
- Complication rate: number of major complications (i.e. perforation, postpolypectomy bleeding requiring hospitalization, and cardiovascular/pulmonary complications requiring medical management) relative to the number of participating individuals.

Differences in these four key outcomes between both strategies will be established by logistic regression analysis, adjusted by age, gender and participating centre, and reported as odds ratios (OR) with 95% CI.

*2. Overall survival at the end of study (10 years)*

*3. CRC incidence at the end of study (10 years and 15 years)*

*4. Cost-effectiveness analysis*

Cost-effectiveness will be studied with a Markov's model at the completion of study. Results will be reported in terms of quality-adjusted life years (QALY).

*5. Analysis of factors influencing participation in the study*

Factors associated with participation at the completion of first round and at the end of study (10 years) in each screening strategies will be analysed by logistic regression analysis and results reported as OR with 95% CI. Parameters analysed will include demographics, personal and familial characteristics, socio-economic status, etc.

*6. Number needed to screen to detect a colorectal cancer*

The number needed to screen to detect a CRC will be calculated using the inverse of risk (i.e. the number of participants receiving a given screening modality divided by the number of positive cases in that given modality), with 95% CI computed using the inverse of the binomial standard approximation.

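### Participants are defined by the assigned arm's own test although cross-over is allowed, so screened switchers can fall out of participation and entry to the detection-rate denominator can depend on the FIT result

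*Combined protocol and SAP*

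**What the plan says.** **Participant rule.** Section 7, secondary end point 1, counts "individuals who completed colonoscopy in the colonoscopy group and individuals who returned the test in the FIT arm". Section 6 gives the same rule for the participant population (wording: "individuals who returned the FIT test (Group 1) or who completed colonoscopy (Group 2"). Participants are the numerator of participation and the denominator of the detection rate and the complication rate. Diagnostic yield uses eligible individuals instead.

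**Cross-over.** The executive summary states: "The study design allowed for cross-over between both screening strategies". Section 4.4 says that people "who do not agree to the type of testing assigned to them may require receiving the alternative test", but that this choice is not actively offered. Section 5 says that such a person "will be assessed according to the group to which he/she was randomised for the “intention to screen” analysis", and by the procedure performed in the as-screened analysis.

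**Analysis sets.** Because of cross-over, Section 7 says that "the main outcomes of the study will be analysed by intention-to-screen, as-screened and per-protocol". The three paragraphs that work out these sets describe Kaplan-Meier risks only. The logistic-regression outcomes under secondary end point 1 have no cross-over rule of their own, and no section says whether a switcher is a participant.

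**The concern.** Section 5 settles which arm a switcher belongs to. It does not settle whether the switcher is a participant in that arm. Applying the participant rule literally by randomised arm gives this:

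- Group 2, FIT on request, negative: screened, but a non-participant.
- Group 2, FIT on request, positive, colonoscopy completed: has completed a colonoscopy in the colonoscopy group, so can be a participant.
- Group 1, straight to colonoscopy: never returned a FIT, so a non-participant even if a cancer is found.

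The Group 2 detection denominator can then admit switchers according to their FIT result. That matches none of the three analysis sets: intention-to-screen would keep all switchers in their arm, as-screened would move them to FIT, and per-protocol would leave them out.

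The outcomes affected are comparative secondary objectives at the first round and at 10 years (Section 3.2). Secondary end point 5, which models factors for participation, would code screened switchers as non-participants.

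**Working it through.** The plan states no participation or detection figure that depends on this rule, so there is nothing to reproduce. The check is algebra followed by an illustration.

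**Algebra, Group 2.** Let E = eligible, C = first-line colonoscopies, X = people who returned a FIT instead, K = those of X who were positive and completed colonoscopy, TP = true positives.

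- Literal rule: participation (C+K)/E; detection TP/(C+K).
- Everyone screened: participation (C+X)/E; detection TP/(C+X).
- TP is the same under both, so literal detection is higher by the factor (C+X)/(C+K), which exceeds 1 whenever K < X.

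**Inputs per 10,000 eligible.** Section 4.8 gives a predictive value of 5-7% for Group 2 and above 40% after a positive FIT; 6% and 40% are used and taken to refer to the same type of lesion. The rest is assumed: C = 1,800 (18%), X = 600 (6%), FIT positivity 5-8%, and all positives complete colonoscopy.

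- K = 600 × 5% = 30 to 600 × 8% = 48.
- TP = 1,800 × 6% + K × 40% = 108 + 12 = 120 to 108 + 19.2 = 127.2.

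| Rule | Participation | Detection rate |
|---|---|---|
| Literal | 1,830 to 1,848 per 10,000 = 18.3-18.5% | 120/1,830 to 127.2/1,848 = 6.6-6.9% |
| Everyone screened | 2,400 per 10,000 = 24.0% | 120/2,400 to 127.2/2,400 = 5.0-5.3% |
| All switchers excluded | 1,800 per 10,000 = 18.0% | 108/1,800 = 6.0% |

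- Against everyone screened, the ratio is 2,400/1,848 to 2,400/1,830 = 1.30-1.31.
- Against excluding all switchers, it is 6.56/6.0 to 6.88/6.0, an overstatement of about 9-15%. This is the part due to selection on the FIT result. The larger ratio also includes dilution by FIT-negative people.
- With 3% cross-over (X = 300, K = 15 to 24), the ratio against everyone screened is 2,100/1,824 to 2,100/1,815 = 1.15-1.16.
- With no cross-over, X = K = 0 and the ratio is 1.

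**Sensitivity to the cross-over share.** Take total Group 2 uptake as 30%, the overall compliance in Section 4.5, and assume FIT positivity of 4-8% and 90% completion of colonoscopy after a positive FIT. With s the share of attenders who switch, the ratio is 1/(1 − s + s × 0.9 × positivity).

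| Share switching | Literal participation (30.0% if all counted) | Detection ratio |
|---|---|---|
| 5% | 28.6% | about 1.05 |
| 10% | 27.1-27.2% | 1.10-1.11 |
| 25% | 22.8-23.0% | 1.30-1.32 |
| 40% | 18.4-18.9% | 1.59-1.63 |

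**Group 1.** Take 30% uptake, a 5% share going straight to colonoscopy, positivity 6%, 90% completion, yield 40% after a positive FIT and 6% in switchers. Per 100 eligible, 28.5 return a FIT and 1.5 switch.

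- Literal participation is 28.5%, against 30.0% counting all screened.
- True positives are 28.5 × 6% × 90% × 40% = 0.6156 from FIT and 1.5 × 6% = 0.09 from switchers.
- Detection is 0.6156/28.5 = 2.16% if switchers' lesions are dropped, 0.7056/28.5 = 2.48% if they stay in the numerator, and 0.7056/30 = 2.35% if all are counted.

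The literal rule can therefore move Group 1 detection either way, depending on a numerator rule that the plan does not state.

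**What does not move.** Group 2 diagnostic yield is 120/10,000 to 127.2/10,000 = 1.2-1.3% under both the literal and the everyone-screened rule. The mortality analysis does not use the participant count.

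**The case against.** The strongest reply is that the result-dependent entry is inferred. No section says that Group 2 FIT takers count only when positive. Sections 4.4 and 5.1 attach colonoscopy after a positive FIT to the FIT strategy, so completing colonoscopy in Group 2 may mean the assigned screening colonoscopy alone. Nothing would then be selected on the FIT result, and the example gives 6.0%. This stands as a possible reading, but it does not close the gap. It still leaves screened switchers out of intention-to-screen participation, and nothing removes their true positives from the numerator. If those stay, detection is 120/1,800 to 127.2/1,800 = 6.7-7.1%.

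Second, uptake of the assigned test is a legitimate measure, and Section 4.6 randomises before invitation so that participation in each group can be assessed. That stands, and is a reason to report it as its own line. Pooling all screened people also blends two tests in one detection rate, which is why test-specific detection belongs in the as-screened analysis.

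Third, the alternative test is given only on request, so cross-over may be rare and the effect small. That stands too.

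A reader might infer that the rule favours colonoscopy in the comparison, or that its detection rate is inflated by 30%. The documents support neither. Group 1 is distorted as well, cross-over rates are not given for either arm, and the 30% rests on an assumed quarter of attenders switching.

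**Conclusion.** The concern holds as a defect in the definition of secondary outcomes. The plan allows cross-over and keeps switchers in their arm, but its participant rule recognises only the arm's own test. Against counting everyone screened, literal use understates participation in both arms whenever people switch. It also overstates Group 2 detection whenever some Group 2 FIT takers do not go on to colonoscopy. The complication rate shares the denominator.

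The size depends on cross-over. The Group 2 detection ratio runs from 1 with none, through about 1.05 at a 5% share of attenders, to about 1.30 at 25%. The direction and size of the net between-arm bias cannot be determined from the documents. This is worth correcting at low cost; it does not threaten the primary result.

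**What to change.** In Section 6 and in secondary end point 1 of Section 7:

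1. For intention-to-screen, define a participant as any eligible person who completed either strategy (returned a FIT or completed a screening colonoscopy), counted in the randomised arm.
2. Put these people's true positives and complications in the matching numerators.
3. Report uptake of the assigned test as a separate line.
4. Report test-specific detection by procedure received in the as-screened analysis.

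The as-screened analysis already needs the procedure performed, so no new data are required. The cost is two reworded definitions and an extra table row. Section 8 places the end of the first round and its interim analysis in mid-2011, so any first-round results already reported under another rule should be labelled as such.

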#### **4.6. Processes of selecting and inviting the population to be screened**

In each Autonomous Region, randomisation will be done prior to sending the invitation letter (Zelen's design) in order to properly assess the participation in each screening group and perform the intention to screen analysis of the results.

The selection process will be the same as the one used in the Nottingham study (14), in which compliance with the programme reached 60%. Briefly, target population will be identified from the Community Health Registry (CHR) of each Autonomous Region. The CHR is based on the population registry, and includes unique identification for each person, such as name, date of birth, social security number, and contact address, and it is updated regularly to account for population migration, deaths and changes in personal details. This list will be refined using cancer registries or other sources of information (primary care medical records, hospital databases, etc.) in order to eliminate individuals who meet exclusion criteria (i.e. CRC and colorectal adenoma) or who have died. Prior to randomisation, individuals will be clustered by household. With such an approach, it is hoped to ensure that all individuals in one household will be assigned to the same study group.

All individuals will receive an initial, pre-invitation letter by mail (which may be signed by their primary care doctor or an area specialist, or the person responsible for the Autonomous Regions screening programme) with information regarding the relevance of CRC as a health problem, the possibility of preventing it by means of screening, and the impending start up of a pilot programme (**presentation letter**), along with an informative leaflet which explains existing measures for CRC prevention. They will later be sent a second letter (also signed by their primary care doctor or area specialist, or the person responsible for the Autonomous Regions screening programme) in which they are invited to participate in the study (**invitation letter**) and includes an appointment to the Local Screening Office (LSO) and a contact telephone number. In the invitation letter, individuals will also be informed of the screening option that applies to them, the characteristics of the test and its possible adverse effects. This whole process will be performed by the LSO (who may be assisted by staff of the project data manager).

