All randomised subjects, whether the appropriate screening strategies have been performed or not, will be followed up for the purpose of tracking changes in the state of their health.

Individuals who are not contacted will be registered for calculation of the invited population.

For subsequent screening rounds, the same system of invitation will be used and according to each Autonomous Region policy.

The CRC prevention units will ensure the performance of colonoscopies no more than 4 weeks after the procedure is indicated. Patients in whom any neoplastic colorectal lesion is detected will be treated and followed up properly.

The treatment of lesions detected in any screening examination will be conducted according to the specific protocol of each centre.

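### Major complications are compared only among participants, which is not a randomised contrast; add a risk difference by assigned arm over all randomised

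*Combined protocol and SAP*

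**What the plan says.** Section 7, Secondary end points, item 1 defines four outcomes. For complications the numerator is major complications and the only denominator is participants: "cardiovascular/pulmonary complications requiring medical management) relative to the number of participating individuals". True positives get two denominators. The detection rate is per participant, and the second measure is "Diagnostic yield: number of true positives relative to the number of eligible individuals". The comparison is the same for all four: "Differences in these four key outcomes between both strategies will be established by logistic regression analysis", adjusted for age, gender and centre and reported as odds ratios.

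Section 6 defines participants as "individuals who returned the FIT test (Group 1) or who completed colonoscopy (Group 2"). It defines an incomplete examination as a "colonoscopy in which caecal intubation is not possible". Section 4.6 states that "randomisation will be done prior to sending the invitation letter".

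Three other places bear on the point:

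- Section 7 opens by applying intention-to-screen, as-screened and per-protocol analyses to the main outcomes. The Intention-to-treat paragraph names CRC incidence and mortality. The Chronogram (section 8) lists the main end point results as CRC mortality, CRC incidence and any-cause mortality.
- Section 5 covers people who take the other test: "Any such individual will be assessed according to the group to which he/she was randomised for the" intention-to-screen analysis, and by the procedure performed for the as-screened analysis.
- Section 5 also says: "All randomised subjects, whether the appropriate screening strategies have been performed or not, will be followed up for the purpose of tracking changes" in health.

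**The concern.** Returning a FIT kit and completing a colonoscopy are different acts, both chosen after randomisation. People who accept one may differ from people who accept the other, and adjusting for three covariates does not restore the randomised comparison. The per-participant rate describes risk for someone who takes a test. It does not estimate what offering one strategy rather than the other does to harm.

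Mortality is to be compared by invitation arm, and diagnostic yield is at least expressed per eligible person. A reader weighing harm against either has no harm estimate on a comparable footing.

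Completeness is also at issue. A logistic model fitted to participants needs each event to belong to a participant. Read literally, the definition can leave out two kinds of harmed person:

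- a Group 1 member harmed at a requested colonoscopy who returned no FIT;
- a Group 2 member whose colonoscopy was stopped by a complication and never completed.

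The first omission flatters FIT and the second flatters colonoscopy, so the net direction is unknown.

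**Working it through.** **No planned figure to reproduce.** The documents give no event count, sample size or power for complications. What follows is a first-round illustration.

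**Inputs from the documents.** N = 27,749 per arm and 30% overall compliance (section 4.5; no figure by arm). Risk per colonoscopy r = 1/2,000 to 2/2,000 (section 2). That risk covers perforation or bleeding only, so every count below omits the cardiovascular and pulmonary events in the end point.

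**Assumptions.** FIT positivity pos = 5–10%. Risk at a post-FIT colonoscopy is k = 1 or 3 times r (section 4.8 says more than half of these examinations involve a therapeutic procedure). Uptake uF (FIT) and uC (colonoscopy) as shown.

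**Expected events at 30/30% uptake**

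- Colonoscopy arm: N × uC × r = 27,749 × 0.30 × r = 4.16 to 8.32.
- FIT arm: N × uF × pos × r × k. Post-FIT colonoscopies number 27,749 × 0.30 × 0.05 = 416 to 27,749 × 0.30 × 0.10 = 832. Events are 0.21–0.83 (k = 1) or 0.62–2.50 (k = 3).

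**Risk differences per 10,000**

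- Per participant: r(1 − pos × k) × 10,000 = 4.5–9.5 (k = 1) or 3.5–8.5 (k = 3), whatever the uptake.
- Per randomised: r(uC − uF × pos × k) × 10,000, tabulated below.

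**Ratios, colonoscopy to FIT.** Per participant the ratio is 1/(pos × k) = 10–20 (k = 1) or 3.3–6.7 (k = 3). Per randomised it is that × uC/uF. The per-participant ratio is therefore the per-randomised ratio × uF/uC.

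| Uptake FIT/colonoscopy | Risk difference per 10,000 randomised, k = 1 | k = 3 | Ratio per randomised, k = 1 | k = 3 | Factor uF/uC |
|---|---|---|---|---|---|
| 30/30% | 1.4–2.9 | 1.1–2.6 | 10–20 | 3.3–6.7 | 1.0 |
| 35/25% | 1.1–2.3 | 0.7–2.0 | 7.1–14.3 | 2.4–4.8 | 1.4 |
| 25/35% | 1.6–3.4 | 1.4–3.1 | 14–28 | 4.7–9.3 | 0.71 |

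**Precision.** With Wilson limits (l, u) for each arm's risk p and d = pC − pF, the Newcombe limits are d − √[(pC − lC)² + (uF − pF)²] and d + √[(uC − pC)² + (pF − lF)²], where the u terms are upper Wilson limits, not uptake. At 30/30% uptake and pos = 10%, per 10,000 randomised:

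| | r = 1/2,000 | r = 2/2,000 |
|---|---|---|
| k = 1 | 1.35 (−0.42 to 3.64) | 2.70 (0.51 to 5.55) |
| k = 3 | 1.05 (−0.91 to 3.37) | 2.10 (−0.38 to 5.01) |

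In the first cell the Wilson intervals are 1.5 (0.594 to 3.790) and 0.15 (0.013 to 1.671). The limits are 1.35 − √(0.906² + 1.521²) = −0.42 and 1.35 + √(2.290² + 0.137²) = 3.64.

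**Events left out by the participant definition**

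- Cross-over: an assumed 1% of the FIT arm is 277 people, carrying 277 × r = 0.14–0.28 events. FIT-arm harm is understated by 1 + 277/(m × k), with m = 416–832: 1.33–1.67 fold (k = 1) or 1.11–1.22 fold (k = 3).
- Stopped colonoscopies: if an assumed share s of colonoscopy-arm complications ends the examination for good, s × (4.16 to 8.32) events are lost and harm is understated by 1/(1 − s). For s = 10% that is 0.42–0.83 events (1.11 fold); for s = 20%, 0.83–1.66 events (1.25 fold).

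**The case against.** **The plan answers its own objective.** Section 3.2 asks to compare yield, participation and incidence, but only to assess the complication rate in each strategy. A rate per person screened does that. This stands, and is why the planned rate should stay. But the SAP goes further and compares the arms on it.

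**The by-arm figure can be derived.** Participation times the complication rate gives complications per eligible person. This stands for the point estimate. It supplies no interval, does not recover harmed people outside the participant set, and uses a denominator also settled after randomisation, since exclusions are confirmed at the appointment (section 4.6).

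**Over all randomised, harm still does not share the yield denominator.** True. It matches mortality, and it is the cleaner contrast.

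**The cross-over rule and intention-to-screen wording already cover this.** The section 5 rule says which group a person counts in. It does not say whether someone who skipped the assigned test is a participant. The main outcomes, as the Chronogram lists them, do not include complications.

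**The omitted people are conjectural.** The numerator is not expressly limited to participants, and incomplete examinations are to be repeated or followed by CT-colonography. Both are fair; hence the claim is only that the wording can omit them. A patient whose colon was perforated may never complete an examination.

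**The gain is small.** Uptake splits, positivity and risk multiples are assumed. At equal uptake the factor is 1.0, and three of the four intervals include zero. Non-participants add almost no events, because harm outside the programme may be under-recorded. All of this stands and limits the weight of the point.

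**Conclusion.** The concern holds, as a minor point on a secondary safety end point. The plan contains no comparison of major complications by assigned arm with an interval, and the odds ratio it does plan is conditional on a choice made after randomisation.

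The direction does not change in any scenario tried: colonoscopy has more expected first-round harm. What changes is the size of the contrast and the completeness of the count. Under the stated assumptions the two ratios differ by 0.71 to 1.4 fold when uptake is split 25/35% either way, and not at all when it is equal. The plan forecasts no uptake by arm, so equality cannot be presumed.

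No 10-year figure was calculated. By then Group 1 will have been offered repeated biennial rounds and Group 2 one screening colonoscopy, yet the same definition serves both time points. The primary mortality conclusion is untouched.

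**What to change.** In section 7, Secondary end points, item 1, keep the per-participant complication rate and its adjusted odds ratio. Add:

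> Complications will also be compared by intention to screen: individuals with at least one major complication from any recorded study colonoscopy (primary, post-FIT, incomplete or repeat, surveillance, or cross-over), counted in the arm assigned at randomisation, divided by all individuals randomised to that arm, as a risk difference per 10,000 with a score (Newcombe) 95% CI, at the end of round one and at 10 years.

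This fixes numerator, denominator, arm and interval without relying on the participant definition. A score interval suits counts this small; the adjusted logistic model may be unstable with fewer than three expected FIT-arm events in the 30/30% illustration.

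The cost is one SAP sentence and one table row. Follow-up of everyone randomised is already planned (section 5), colonoscopy reports record immediate complications (section 4.8), and test results and treatments go to the central database (section 5.2). Three limits should be stated with the result: the interval will be wide; events at examinations outside the programme may be missed, because non-participants' long-term status comes from population registries (section 4.4); and the interval ignores household grouping, which should matter little for events this rare.
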